- to test the hypothesis that suppressive treatment for 12 months with oral valacyclovir 1000 mg daily reduces the incidence, severity and duration of post herpetic neuralgia (PHN) compared to placebo at 12 and 18 months in study participants with HZO.
- to test the hypotheses that vaccination against herpes zoster with the Recombinant Zoster Vaccine
 (RZV) may impact the natural history of HZO, and that suppressive antiviral treatment with
 valacyclovir 1000 mg daily compared to placebo may alter the impact of this vaccination on HZO
 activity during 12 months of study treatment.

See sections 4.2.2 for details regarding additional objectives.

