4.2.2 SECONDARY ENDPOINTS

To assess the secondary objectives, the study participants will be monitored at each visit for the following events:

- Time to development and number of episodes of new or worsening dendriform epithelial keratitis, stromal keratitis, endothelial keratitis, and/or iritis due to HZO, requiring pre-specified changes in treatment (see MOP), during the 18 months following randomization, that includes the 6 months following cessation of treatment; and during the 6 months following the end of the 12 month treatment period.
- 2. The incidence, severity, and duration of PHN at one year of treatment, and after the 6-month post-treatment follow up.
- 3. Impact of Recombinant Zoster Vaccine (RZV) vaccination on primary endpoints during 12 months of study treatment.

- 4. Development of specific manifestations of HZO, classified as dendriform epithelial keratitis, stromal keratitis (all types), endothelial keratitis, iritis requiring pre-specified changes in treatment (see MOP), neurotrophic keratopathy with or without melting and/or microbial superinfection, episcleritis, and/or scleritis during the twelve months of treatment.
- 5. Secondary glaucoma determined by IOP and treatment required.

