7.1 STUDY PROCEDURES/EVALUATIONS

7.1.1 STUDY SPECIFIC PROCEDURES

The following procedures will be performed for study-specific purposes:

- · Review of inclusion/exclusion criteria for eligibility
- Informed consent
- Collection of demographic information
- eGFR and Pregnancy Tests
- Collection of HZO treatment information
- Randomization: Eligible participants will be randomized to receive either valacyclovir or matching placebo.
- Study specific history: assessment of post herpetic neuralgia using question #3 of Zoster Brief Pain Inventory (ZBPI)
- Study specific ophthalmic exam of the eye with HZO
- Completion of medical event form
- Collection of information regarding any serious adverse events (SAEs)
- Assessment of study adherence: counts of returned unused pills and study participants diary card records.
- Monthly contact between study visits, eg. telephone, email, text, or letter is encouraged. (See MOP)

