7.3.3 FOLLOW-UP STUDY VISITS

Study visit number at 3, 4, 5 occurring at months 3, 6, and 9 after enrollment:

At the follow-up visits, the following activities will occur/be performed:

- Study specific history of HZO treatment.
- Study specific anterior segment ophthalmic exam.
- Assessment of post herpetic neuralgia score and review of medications taken for PHN.
- Returned study medication pills will be counted to assess medication compliance. Diaries will be returned.
- Assessment for possible medical events of interest
- Assessment for possible primary endpoints.
- Assessment for possible SAEs.
- Study participants will be dispensed an adequate supply of study medication and will receive instructions to take 2 pills once daily. in addition to any other medication(s). At the discretion of the investigator, dosage may be adjusted to one pill twice daily or once daily and appropriate study participant instruction sheet will be provided (see MOP).
- Study participants will receive a diary to record when study medication is taken.
- If the study participant had a baseline eGFR of 45-59 repeat eGFRs will be completed prior to the 3, 6, 9 month study visits.
 - o If eGFR is 45 or above, study medication will be continued.
 - If eGFR is less than 45, the study medication will be discontinued, and the eGFR will be repeated within one week. If on repeat testing the eGFR:
 - is 45 or more, the study medication will be resumed, and eGFR will be repeated within 30 days of the next study visit.
 - is less than 45, study participant will be given a prescription to visit their local study designated laboratory for monthly eGFR testing until it is 45 or more. In addition, study participants will be told to see their primary care doctor for management of their kidney disease. The study medication will not be resumed, and the study participant will continue to be followed in the study.
- An appointment to return during a specified window of days for their three-month follow-up visit will be scheduled.
- The study participant will be instructed to continue their non-study treatment.

The importance of compliance with the study medication and visits, will be emphasized at each study visit. Study participant's contact information will also be confirmed at each study visit (see MOP).

Visit 6 (12 month follow-up visit):

At this visit, study medication will be discontinued. The visit will be the same as the 3, 6, and 9- month follow-up visits, with the addition of:

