7.3.7 SCHEDULE OF EVENTS TABLE

Source documents include medical records, images and all other information necessary to reconstruct and evaluate the clinical trial. Study monitors will compare data entered in electronic CRF's to information in source documents to verify the accuracy of trial data.

Please see Table 1 for Schedule of Events.

Table 1: Schedule of Events.

Procedures	Screening/consent (Visit 1)	Enrollment/Randomization (Visit 2)	3-month Follow-up (Visit 3)	6-month Follow-up (Visit 4)	9-month Follow-up (Visit 5)	12-month Follow-up (Visit 6)	15-month Follow-up (Visit 7)	18-month Follow-up (Visit 8)
Informed consent	X							
Study specific review of medical records ¹	Х	х						
Study specific review of demographics	Х							
Review of inclusion/exclusion criteria ²	Х	х						
Order pregnancy test ³	Х							
Order serum creatinine blood test for eGFR determination ⁴	X ^{4,5}							
Repeat eGFR prior to visit only if baseline eGFR = 45-59 ⁵			х	х	х	х		
Study specific history of HZO treatment		х	Х	х	х	х	х	Х
Study specific ophthalmic exam		X^6	X ⁷	X ⁷	X ⁷	X ⁸	X ⁷	X ⁷
PHN score and review of medication history for PHN		Х	Х	Х	Х	Х	Х	Х
Randomization		х						
Medication dispensed and instruction sheet provided		х	х	х	х			
Assessment of possible medical events			х	х	х	х	х	Х
Assessment of possible primary endpoints			х	х	х	Х	х	Х
Assessment of possible SAEs			Х	Х	Х	Х	Х	Х

¹ Study specific review of the participant's medical history is reviewed at the screening visit and the case report form is completed at the enrollment visit. If the study participant is ineligible, the form is not completed.

² Inclusion/exclusion criteria are reviewed at the screening visit and the case report form is completed during the enrollment visit. If the study participant is ineligible at the screening visit, the form is completed then.

³ A serum pregnancy test is required of women of child-bearing potential, who have provided written informed consent and are found to be eligible. The pregnancy test should preferably be done 2-3 days after a menstrual cycle. A urine dipstick test for pregnancy will be conducted by study staff if a study participant suspects pregnancy at the time of a study visit.

⁴ A serum creatinine blood test for eGFR determination will not be required if one has been completed in the past 30 days and the results are available for review.

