10.2 STATISTICAL HYPOTHESES

The primary objective of this randomized controlled clinical trial is to test the hypothesis that long-term suppressive antiviral treatment for 1 year with oral valacyclovir 1000 mg daily delays the time to the first occurrence of new or worsening anterior segment ocular disease (*dendriform epithelial keratitis*, *stromal keratitis*, *endothelial keratitis*, *and/or iritis*) compared to placebo by 12 months.

The secondary objectives are (1) a) to test the hypothesis that long-term suppressive antiviral treatment for 1 year with oral valacyclovir 1000 mg daily delays the time to the first occurrence of new or worsening anterior segment ocular disease (*dendriform epithelial keratitis, stromal keratitis, endothelial keratitis, and/or iritis*) compared to placebo by 18 months; and b) to test the hypothesis that the occurrence of new or worsening disease in the 6 months post treatment period is reduced for participants treated with valacyclovir compared to placebo; and (2) to test the hypothesis that suppressive treatment for 12 months with oral valacyclovir 1000 mg daily reduces the

incidence, severity and duration of post herpetic neuralgia (PHN) compared to placebo at 12 and 18 months in patients with HZO.

To evaluate these hypotheses, the following endpoints will be evaluated:

Primary Efficacy Endpoint:

The primary endpoint is the time to first occurrence of new or worsening episode of dendriform epithelial keratitis, stromal keratitis, endothelial keratitis, and/or iritis due to HZO, accompanied by pre-specified changes in treatment for the same disease manifestation of HZO (see MOP) during the twelve months of treatment. The primary endpoint is compared for participants randomized to study medication or placebo.

To assess the primary objectives, study participants will be monitored at each visit for new or worsening any of the following conditions (see MOP for definitions):

- 1. Dendriform epithelial keratitis:
- 2. Stromal keratitis
 - a. Without ulceration
 - b. With ulceration
- 3. Endothelial keratitis
- 4. Iritis

The endpoint of first occurrence of new or worsening dendriform epithelial keratitis, stromal keratitis, endothelial keratitis, and/or iritis will be determined by clinical examination accompanied by prespecified changes in treatment (see MOP), as there are no validated confirmatory biomarkers or other tests.

Secondary Efficacy Endpoints:

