To assess the secondary objectives, the study participants will be monitored at each visit for the following:

- Time to development and number of episodes of new or worsening dendriform epithelial keratitis, stromal keratitis, endothelial keratitis, and/or iritis due to HZO, requiring pre-specified changes in treatment (see MOP), during the 18 months following randomization, that includes the 6 months following cessation of treatment; and during the 6 months following the end of the 12 month treatment period.
- 2. The incidence, severity, and duration of PHN at one year of treatment, and after the 6 month post-treatment follow up.
- 3. Impact of vaccination against zoster with RZV on outcomes.
- 4. Development of specific manifestations of HZO, classified as dendriform epithelial keratitis, stromal keratitis (all types), endothelial keratitis, iritis requiring pre-specified changes in treatment (see MOP), neurotrophic keratopathy with or without melting and/or microbial superinfection, episcleritis, and/or scleritis during the twelve months of treatment.
- 5. Secondary glaucoma as determined by IOP and treatment required.

Exploratory Efficacy Endpoints:

- 1. Changes in strength and/or frequency of prescribed topical corticosteroids at 12 and 18 months.
- 2. Occurrence of stroke
- 3. Occurrence of temporal arteritis/giant cell arteritis
- 4. Occurrence of myocardial infarction

- 5. Occurrence of new or worsening malignancy
 - a. Solid tumor (other than non-melanoma skin cancer)
 - b. Hematologic malignancy
 - c. Lymphoma.
- 6. Time to development and number of episodes of new or worsening dendriform epithelial keratitis, stromal keratitis, endothelial keratitis, and/or iritis due to HZO, with a recent substantial reduction in treatment (see MOP) during 12 months of treatment.
- 7. Impact of suppressive antiviral treatment prior to enrollment on outcomes during 12 months of study treatment.

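### Does the lack of a named zoster-vaccination item in the visit schedule leave the RZV secondary objective without data?

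*Combined protocol and SAP*

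**What the plan says.** The secondary objectives in Section 3 include a vaccine objective with two parts: whether RZV changes the natural history of HZO, and whether "valacyclovir 1000 mg daily compared to placebo may alter the impact of this vaccination on HZO" activity during the 12 months of study treatment.

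Section 4.2.2 says that, for the secondary objectives, "the study participants will be monitored at each visit for the following events". Its third item is "Impact of Recombinant Zoster Vaccine (RZV) vaccination on primary endpoints during 12 months of study treatment". Section 10.2 repeats the each-visit lead-in, and its third item is "Impact of vaccination against zoster with RZV on outcomes".

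The paragraph of 10.2 that states the secondary objectives opens with "The secondary objectives are (1) a) to test the hypothesis that long-term suppressive antiviral treatment for 1 year" and ends with postherpetic neuralgia (PHN). It has no RZV item.

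On data collection, the nearest entries are general ones: "Completion of medical event form" in 7.1.1 and "Assessment for possible medical events of interest" in 7.3.3. Other secondary data have their own line at each follow-up visit, such as the Table 1 row "PHN score and review of medication history for PHN".

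**The concern.** Both RZV hypotheses need to know who was vaccinated, with which product and when. RZV is not randomised and can be given during the study, so each flare must be placed before or after a dose. A reader who goes from Section 3 to the visit procedures finds named lines for HZO treatment, the eye examination and PHN, and none for vaccination.

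Other routes do not obviously fill the space. Under 6.1.8 the live vaccine interrupts study medication but RZV does not, so an RZV dose leaves no trace in the dosing record. Section 8.1.1 requires adverse-event reports only where study medication is stopped. Table 1 has no general concomitant-medication row.

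If doses were noted only when they happened to come up, exposure would be incomplete and power would fall. If they came up more often in participants who flared, an inert vaccine could appear to provoke flares. The two versions of endpoint 3, and the gap in the 10.2 objectives, add doubt about what is to be estimated.

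**Working it through.** **The plan's own figure.** The documents give no sample size, power or effect size for RZV. The only figure is the primary one in 10.5: 390 per arm, 12-month failure 30% against 21.3%, two-sided alpha 0.05, 80% power.

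- Hazard ratio: ln(1 − 0.213) / ln(1 − 0.30) = 0.672 (stated: 0.67).
- Expected first events: D = 390 × (0.30 + 0.213) = 200.
- Log-rank power: Φ(|ln 0.672| × √(200/4) − 1.96) = 80.4% (stated: 80%).

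The figure reproduces. The stratified log-rank test in 10.4.2 uses age at onset and recent or chronic disease, with no vaccination term. The vaccine question therefore cannot move it.

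**The count.** Section 7.1.1 has 12 items and Table 1 has 15 rows. Neither names vaccination, nor do the visit lists in 7.3.1 to 7.3.4 or the Table 1 footnotes. So far the concern is right on the text.

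**Does absence from these lists mean the data are not collected?** Compare other data that the protocol plainly needs:

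- Intraocular pressure defines secondary endpoint 5 in 4.2.2 and 10.2, but no examination list in 7.3.2, 7.3.3 or the Table 1 footnotes mentions it.
- Stroke, myocardial infarction, temporal arteritis and malignancy are exploratory endpoints in 4.2.3, but neither 7.1.1 nor Table 1 names them.
- Section 6.1.8 says open-label antiviral use is collected and centrally monitored, but it has no row of its own.
- Pill counts are in 7.1.1 and 7.3.3 but not in Table 1.

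The lists are headings, not field inventories. A count of 0 of 15 and 0 of 12 describes the headings.

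**What elsewhere implies that vaccination is recorded?**

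- The lead-ins to 4.2.2 and 10.2 call for monitoring at each visit.
- Section 10.4.9 plans analyses of primary and secondary endpoints by zoster vaccination status, so the sponsor expects to hold that variable.
- Exclusion 5 in 5.2 sets rescreening for RZV recipients at one month after the second dose. Applying it requires product, dose number and date.
- Section 6.1.8 treats the two vaccines differently, so a site told of a vaccination must identify the product.
- Section 14.1 provides a visit checklist so that all required data are obtained at each visit, with procedures in the MOP.

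**The 10.2 wording.** The objectives paragraph lists two objectives. The same section then says which endpoints will address its hypotheses, and RZV is the third secondary endpoint. The analysis is therefore still announced. Section 4.2.2 gives the narrower definition (primary endpoint, 12 months), which agrees with the 12-month window in Section 3. An analyst would use that one.

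**The case for a change.** The strongest case for acting is that the omission is cheap to repair and costly to find late. Accrual is put at 7 years in 10.5, and dose dates not asked for now would have to be recovered by recall. Recording that differs by outcome can mislead. Take an inert vaccine, assumed uptake of 20, 40 or 60%, n = 780 and the 10.5 failure rates. If vaccination is recorded in 90% of participants with an endpoint and 70% without, the apparent hazard ratio is 1.28, 1.31 or 1.37, with false-positive rates of 18, 31 and 47%. With equal recording it is 0.98 to 1.02, with 5 to 6%.

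What stands is the principle that ascertainment should be the same for everyone. The sizes do not stand as a measure of this trial, because the documents give no uptake and no recording rates. The proposed mechanism is also weak. Section 7.3.6 has a form completed at every non-study visit and says more may be needed when an endpoint is possible, but nothing says those forms ask about vaccines. Under 5.4.1, participants are followed on the same schedule whether or not they have reached the endpoint. Adding a vaccine question at unscheduled visits could itself create the imbalance, since participants who flare plausibly have more of them.

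A second argument is that the valacyclovir-by-vaccine hypothesis has little power. With 200 events and at best half of them in vaccinated time, the variance of the log ratio of hazard ratios is at least 16/200. Power for a ratio of 0.67 is then at most Φ(0.400/0.283 − 1.96) = 29%. That is true, but it has no bearing on whether doses are recorded. The protocol claims no power for this non-randomised question.

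**Conclusion.** No change to the plan is called for. The textual points are correct: no procedure list names vaccination, the 10.2 objectives omit RZV, and endpoint 3 is worded in two ways. The first is detail left to working documents, which a team following the each-visit instruction would supply. The other two are clerical, and Section 3 with 4.2.2 settles the intended endpoint and window.

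The effect on the primary comparison is nil. For the RZV objective, no loss of data has been shown and no size can be put on one from the documents.

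This rests on one assumption: that the MOP, case report forms or visit checklist hold vaccine type and dose dates, asked in the same way of all participants. Those papers were not available, nor was any detailed SAP text on RZV, to which 10.4.3 defers the methods. If the forms proved to have no such field, the conclusion for this secondary objective would have to be reopened.

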4 STUDY DESIGN AND ENDPOINTS

4.1 DESCRIPTION OF THE STUDY DESIGN

The study is a double-masked, multi-center RCT that will enroll immunocompetent study participants age 18 years and older who have HZO diagnosed at variable times in the past, with an episode of dendriform epithelial keratitis, stromal keratitis, endothelial keratitis, and/or iritis within one year of enrollment. Eligible study participants will be randomized in a 1:1 ratio to long-term suppressive treatment with oral valacyclovir 1000 mg

daily or placebo for one year, and followed every 3 months for a total of 18 months, to determine outcomes of new or worsening anterior segment ocular disease (e.g. dendriform epithelial keratitis, stromal keratitis, endothelial keratitis, and/or iritis) and/or severity and duration of postherpetic neuralgia during 12 months of treatment and for 6 months following treatment discontinuation. Within each center, participants will be randomized within four strata, defined by age at onset of HZO (less than 60 years or 60 years and greater) and by recent onset or chronic HZO (recent onset defined as HZO diagnosed within 6 months of enrollment/randomization, or chronic defined as HZO diagnosed 6 months or more prior to enrollment/randomization).

4.2.1 PRIMARY ENDPOINT

The primary endpoint is the time to first occurrence of new or worsening episode of dendriform epithelial keratitis, stromal keratitis, endothelial keratitis, and/or iritis due to HZO, requiring pre-specified changes in treatment (see MOP) during the twelve months of treatment. The primary endpoint is compared for participants randomized to study medication or placebo.

To assess the primary objectives, study participants will be monitored at each visit for new or worsening of any of the following conditions

- 1. Dendriform epithelial keratitis
- 2. Stromal keratitis
 - a. Without ulceration
 - b. With ulceration
- 3. Endothelial keratitis
- 4. Iritis

The endpoint of first occurrence of new or worsening dendriform epithelial keratitis, stromal keratitis, endothelial keratitis, and/or iritis will be determined by clinical examination requiring pre-specified changes in treatment for the same disease manifestation (see MOP for definition), as there are no validated confirmatory biomarkers or other tests. Primary endpoints will be reviewed by Clinical Event Review Committee (CERC). See MOP.

4.2.2 SECONDARY ENDPOINTS

To assess the secondary objectives, the study participants will be monitored at each visit for the following events:

- Time to development and number of episodes of new or worsening dendriform epithelial keratitis, stromal keratitis, endothelial keratitis, and/or iritis due to HZO, requiring pre-specified changes in treatment (see MOP), during the 18 months following randomization, that includes the 6 months following cessation of treatment; and during the 6 months following the end of the 12 month treatment period.
- 2. The incidence, severity, and duration of PHN at one year of treatment, and after the 6-month post-treatment follow up.
- 3. Impact of Recombinant Zoster Vaccine (RZV) vaccination on primary endpoints during 12 months of study treatment.

- 4. Development of specific manifestations of HZO, classified as dendriform epithelial keratitis, stromal keratitis (all types), endothelial keratitis, iritis requiring pre-specified changes in treatment (see MOP), neurotrophic keratopathy with or without melting and/or microbial superinfection, episcleritis, and/or scleritis during the twelve months of treatment.
- 5. Secondary glaucoma determined by IOP and treatment required.

4.2.3 EXPLORATORY ENDPOINTS

- 1. Changes in strength and/or frequency of prescribed topical corticosteroids at 12 and 18 months.
- 2. Occurrence of stroke
- 3. Occurrence of temporal arteritis/giant cell arteritis
- 4. Occurrence of myocardial infarction
- 5. Occurrence of new or worsening malignancy
 - a. Solid tumor (other than non-melanoma skin cancer)
 - b. Hematologic malignancy
 - c. Lymphoma
- 6. Time to development and number of episodes of new or worsening dendriform epithelial keratitis, stromal keratitis, endothelial keratitis, and/or iritis due to HZO, with a recent substantial reduction in treatment during 12 months of treatment.
- 7. Impact of suppressive antiviral treatment prior to enrollment on study outcomes.

Rates of these events will be estimated among study participants randomized to valacyclovir and placebo.

